### **2.4 Treatment Regimens**

At randomization for the crossover phase, subjects will be assigned in a 1:1:1:1 ratio to one of four arms:

- MS1819 (2240 mg/day) followed by prestudy porcine PERT
- Prestudy porcine PERT followed by MS1819 (2240 mg/day)
- MS1819 (4480 mg/day) followed by prestudy porcine PERT
- Prestudy porcine PERT followed by MS1819 (4480 mg/day)

MS1819 will be administered in enteric capsules for the crossover phase. Subjects will receive the same dose of PERT that was being administered during the prestudy period while in the porcine PERT period of their treatment sequence.

The extension phase will enroll patients as follows:

- 9 patients will be enrolled initially, each receiving 4.4 grams/day of MS1819 IR
- Based on resulting CFA data, 5 additional patients may be enrolled, each receiving 4.4 grams/day of MS1819 IR
- If safety in the 4.4 grams/day dose is found to be satisfactory and the CFAs do not achieve values in the therapeutic range, 9 patients will be enrolled, each receiving 6.7 grams/day of MS1819 IR
- Based on resulting CFA data, 5 additional patients may be enrolled, each receiving 6.7 grams/day of MS1819 IR

MS1819 will be administered in IR capsules for the extension phase.

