## 8. SAFETY EVALUATION

### 8.1 Overview of Safety Analysis Methods

Unless otherwise stated, safety analyses will be presented separately for each dose of the crossover phase and each dose of the extension phase. For the crossover phase, all safety analyses will be performed using the safety population and summarized by actual treatment (MS1819 regardless of period vs. PERT regardless of period) allowing direct intrasubject comparison of the tolerability of MS1819 vs. PERT. For the extension phase, all safety analyses will be performed using the safety population and summarized for each dose. Safety measures summarized will include AEs, laboratory data, vital signs, and concomitant medications. Additionally, exposure to study treatment during the study will be displayed.

Safety data will not be imputed, except for partial and missing dates, which will be imputed only for defining treatment-emergent AEs (TEAEs) and concomitant medications. Imputed dates will not be presented in data listings.

TEAEs will be defined as any AEs that occur or are reported to worsen in severity on or after the date of first dose of study treatment in crossover phase period 1. Partial dates will be imputed for the purposes of defining TEAEs as follows:

- For a missing start day where the month and year are present, the start day will be set to the first day of the month, unless 1) the first day of the month is before the date of first dose of study treatment and the month and year are the same as the month and year of the date of first dose of study treatment, and 2) the end date is on or after the date of first dose of study treatment or the end date is completely missing, in which case the start day will be set to the first day of first dose of study treatment.
- For a missing start day and month where the year is present, the start day and month will be set to January 1st, unless 1) January 1st is before the date of first dose of study treatment and the year is the same as the year of the date of first dose of study treatment, and 2) the end date is on or after the date of first dose of study treatment or the end date is completely missing, in which case the start day and month will be set to that of the date of first dose of study treatment.

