- For a missing end day where the month and year are present, the end day will be set to the last day of the month, unless the month and year are the same as the month and year of the last contact date for the subject, in which case the end day will be set to that of the subject's last contact date.
- For a missing end day and month where the year is present, the end day and month will be set to the subject's last contact date, unless the year of the subject's last contact date is greater than the end year, in which case the end day and month will be set to December 31st.

To categorize events with partial dates into their associated treatment periods, the imputation rules above will be defined relative to the first dose of the treatment period of interest separately (first treatment period of crossover, second treatment period of

crossover, 4.4 grams/day dose stage of the extension phase, 6.7 grams/day dose stage of the extension phase), as applicable. Thus, in the aforementioned rules, ‘study treatment’ refers to the treatment in the specified treatment period. Per the imputation rules, events with partial dates may require multiple imputed start dates to account for each treatment period. For example, an event with missing start day where the start month is the same as the treatment start month for both study treatments of the crossover period will have the start date imputed to both the treatment start date of the first crossover study period and the treatment start date of the second crossover study period.

Partial and completely missing dates will be imputed for the purposes of classifying concomitant medications as follows:

- Partial dates will be imputed following the same algorithm as above for TEAEs.
- For a missing start date (i.e., day, month, and year are missing), the start date will be set to the date of first dose of study treatment for each period (first treatment period of crossover, second treatment period of crossover, first dose period of the extension phase, second dose period of the extension phase), as applicable, unless the stop date is prior the date of first dose of study treatment for a given period, in which case the start date will be set to the stop date.
- For a missing stop date (i.e., day, month, and year are missing), the medication will be treated as ongoing.

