## 8.3 Adverse Events

Adverse events will be coded using the Medical Dictionary for Regulatory Activities (MedDRA) Version 23.0 to identify the system organ class and preferred term.

Adverse events that occur or are reported to worsen in severity on or after date of first dose of study treatment in crossover phase period 1 will be considered to be TEAEs.

TEAEs will be categorized as occurring in a given study period according to the following rules:

- Adverse events that occur or are reported to worsen in severity on or after date and time of start of crossover period 1 study treatment and on or before date and time of end of crossover period 1 study treatment will be attributed to crossover study period 1. Adverse events that occur or are reported to worsen in severity on the start date of crossover period 1 study treatment that do not have a time associated with the event will be attributed to crossover study period 1.
- Adverse events that occur or are reported to worsen in severity after the end date of crossover period 1 study treatment and on or before the date of end of crossover period 2 study treatment will be attributed to crossover study period 2. Adverse events that occur or are reported to worsen in severity on the date of end of crossover period 2 study treatment that do not have a time associated with the event will be attributed to crossover study period 2.
- Adverse events that occur on the crossover date between crossover study period 1 and crossover study period 2 that do not have a time associated with the event will be attributed to crossover study period 1.
- Adverse events that occur in both crossover study period 1 and crossover study period 2 will be attributed to both crossover study periods.

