- Adverse events that occurred after the subject's last crossover study period will be classified as follow-up adverse events. If a subject entered both the first and second study periods, events occurring after the end date of the second study period will be considered as follow-up. If a subject discontinued prior to the start of the second crossover study period, any event occurring after the end date of the first crossover study period will be considered as follow-up. For subjects that did not enroll in the extension phase, any adverse event following the last crossover study period will be categorized as follow-up adverse events of the crossover phase. For subjects that did enroll in the extension phase, adverse events that occurred after the last crossover study period but before the start of the extension phase will be categorized as follow-up adverse events of the crossover phase.

The same period categorization rules will apply for the extension phase, where applicable, with the following exception. For the extension phase, if a subject only participates in the 4.4 grams/day dose stage of the extension phase, adverse events will only be categorized into the 4.4 grams/day treatment period or follow-up period within the extension phase. Otherwise, adverse events will be categorized into the 4.4 grams/day dose stage, the 6.7 grams/day dose stage, and follow-up as described above. For example, an adverse event that occurs in both the 4.4 grams/day dose period and the 6.7 grams/day dose period will be attributed to both extension phase treatment periods.

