#### **8.4 Deaths, Serious Adverse Events, and Other Significant Adverse Events**

Treatment-emergent SAEs, TEAEs leading to study discontinuation, TEAEs resulting in death, treatment-emergent SAEs by relatedness, treatment-emergent SAEs leading to discontinuation, and treatment-emergent SAEs resulting in death will be summarized for all subjects in the safety population for each study phase. Summary tables will reflect a count and percentage of subjects experiencing at least 1 TEAE in each system organ class and preferred term within each AE subset (serious, leading to discontinuation, death). These summaries will be presented by treatment group and overall for each dose in the crossover phase and overall for each dose in the extension phase with percentages that

use the number of subjects in the safety population as the denominator. These tabular summaries will be sorted by descending frequency by system organ class and by preferred term in the MS1819 treatment group.

Adverse events leading to study discontinuation, AEs resulting in death, and SAEs will be presented in data listings for subjects in the safety population for each dose of the crossover phase and for each dose of the extension phase.

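### SAP 8.3 can count an adverse event left over from crossover period 1 under both treatments, which blurs the MS1819 versus PERT tolerability tables; attribute by treatment at onset or worsening

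*SAP*

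**What the plan says.** SAP 8.1 sets the principle for treatment emergence, with the start of crossover period 1 as the reference point: "TEAEs will be defined as any AEs that occur or are reported to worsen in severity on or after the date of first dose". It also says that crossover safety data are "summarized by actual treatment (MS1819 regardless of period vs. PERT regardless of period) allowing direct intrasubject comparison of the tolerability of MS1819 vs. PERT".

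SAP 8.3 then sorts events into periods. The first bullet gives period 1 the events that start or worsen during period 1 treatment. The second does the same for period 2, beginning "Adverse events that occur or are reported to worsen in severity after the end date of crossover period 1 study treatment". The third sends untimed events on the crossover date to period 1 only. The fourth reads: "Adverse events that occur in both crossover study period 1 and crossover study period 2 will be attributed to both crossover study periods". The extension phase follows the same rules, with the example that "an adverse event that occurs in both the 4.4 grams/day dose period and the 6.7 grams/day dose period will be attributed to both".

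SAP 8.1 adds that "events with partial dates may require multiple imputed start dates to account for each treatment period". For the SAE, discontinuation and death tables, SAP 8.4 says: "These summaries will be presented by treatment group and overall for each dose in the crossover phase". Protocol 7.1 plans no washout between the crossover periods.

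**The concern.** The first two bullets already place any event that starts or worsens in a period into that period. If the fourth bullet adds anything to them, the natural candidate is an event that began in period 1 and was still open, without worsening, when treatment changed. The SAP does not define occurring in both periods, and it specifies no onset-only table.

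On that reading an event is counted once under each treatment. A PERT-first patient whose event began before any MS1819 dose enters the MS1819 column. An MS1819-first patient whose event began on MS1819 enters the PERT column. Neither count fits the SAP's own principle of onset or worsening.

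Safety is a primary objective, and these are the tables offered as an intrasubject comparison. The DSMB's planned end-of-study review draws on a subset of them (SAP 10.1). With 15 patients per dose, one carried-over patient moves a column by 1/15 = 6.7 points.

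**Working it through.** **Reading the bullet.** For the wider (spanning) reading: bullets one and two already cover onset and worsening, and the extension example speaks of a single event found in two dose periods. For the narrower reading: the bullet could simply confirm that an event with onset in period 1 and worsening in period 2 counts twice, or cover an event given an imputed start date in each period. The wider reading is likelier, but the text does not settle it.

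**Inputs from the documents.** Allocation: "subjects will be assigned in a 1:1:1:1 ratio to one of four arms" (SAP 2.4), so half of each dose group is PERT-first. Planned size is 15 patients per dose (SAP 2.6). No AE rate, persistence rate or AE contrast is given, so there is no planned figure to reproduce.

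**Assumptions.** pM and pP are the proportions of patients with an event starting on MS1819 and on PERT. qM and qP are the shares of such period 1 events still open in period 2. Sequences are equal in size, every patient enters both periods, and periods are independent.

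**Formulae (wider reading).** A patient enters the MS1819 column with an MS1819-onset event. A patient without one also enters if PERT-first with a PERT-onset event that persisted. The PERT column mirrors this.

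- MS1819 tabulated = pM + ½·qP·pP·(1 − pM)
- PERT tabulated = pP + ½·qM·pM·(1 − pP)

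With qM = qP = q, the difference is (pM − pP) + ½·q·[pP(1 − pM) − pM(1 − pP)] = (pM − pP)(1 − q/2).

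**Numbers for assumed pM = 40%, pP = 20% (onset difference 20.0 points).** For example, at q = 50%: MS1819 = 0.40 + 0.5 × 0.5 × 0.20 × 0.60 = 0.430; PERT = 0.20 + 0.5 × 0.5 × 0.40 × 0.80 = 0.280.

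| qM | qP | MS1819 | PERT | Difference (points) |
|---|---|---|---|---|
| 10% | 10% | 40.6% | 21.6% | 19.0 |
| 25% | 25% | 41.5% | 24.0% | 17.5 |
| 50% | 50% | 43.0% | 28.0% | 15.0 |
| 10% | 50% | 43.0% | 21.6% | 21.4 |
| 50% | 10% | 40.6% | 28.0% | 12.6 |

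**In patients, out of 15.** At q = 50%, MS1819 goes from 6.0 to 6.45 and PERT from 3.0 to 4.20. The difference falls from 3.0 to 2.25, a shift of 0.75. At q = 25% the shift is 0.025 × 15 = 0.375; at 10% it is 0.01 × 15 = 0.15. In the last row it is 0.074 × 15 = 1.11.

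**Direction.** PERT-to-MS1819 carry-over alone raises only the MS1819 column, so the gap widens to 20.6, 21.5 or 23.0 points at qP = 10%, 25% or 50%. The shrinkage comes from MS1819-onset events counted under PERT. With both flows, the gap widens when qP × 0.20 × 0.60 exceeds qM × 0.40 × 0.80, that is, when qP is more than 0.32/0.12 = 2.67 times qM. If both rates are 30% and persistence is equal, the difference stays at zero.

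**The case against.** The narrower reading has real support. SAP 8.1 and 8.3 repeatedly set occurring against worsening, which suggests that occurring means onset. The untimed switch-day bullet makes most sense as an onset rule. Where the SAP wants ongoing status to count, it says so, as for concomitant medications in SAP 8.6.3.1. A reader might infer that the bullet can only add unresolved, non-worsening events; the documents do not support that, because onset plus worsening and doubly imputed dates also fit. What remains is an undefined term that two programmers could implement differently.

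There are mitigations. Relatedness is scored separately for MS1819 and PERT, SAEs are tabulated by relatedness, and all AEs are listed. Worsening of EPI is not an AE unless serious (Protocol 9.1.1), which removes an obvious source of lingering events. These limit the volume but do not correct the overall TEAE tables, which ignore relatedness. Also, SAP 8.3 sets missing relatedness to the maximum, so a carried-over PERT-onset event left unscored for MS1819 would show as MS1819-related.

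Counting spanning events under both treatments can be defended as conservative. A strict onset rule has its own fault: an event that began on PERT, persisted unchanged and led to withdrawal on MS1819 would vanish from the MS1819 discontinuation table. That objection stands, and the fix has to deal with it.

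**Conclusion.** The point holds as a cheap improvement to a primary-objective table. On the likelier reading, SAP 8.3 puts PERT-onset events in the MS1819 column and MS1819-onset events in the PERT column, against the SAP's own onset-or-worsening principle.

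The size is modest. With equal persistence up to 50% at the assumed rates, the difference moves by at most 0.75 of a patient in 15, although the PERT column alone can rise by 1.2. The factor (1 − q/2) rests on similar persistence on both treatments, independent periods and equal sequences; the rates and q are assumptions.

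Three stronger inferences are tempting and are not supported.

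- That the rule always pulls the contrast toward zero: with unequal persistence it can widen.
- That PERT-onset events counted under MS1819 cause the shrinkage: if MS1819 has the higher rate, that flow alone widens the gap.
- That the extension is affected equally: patients return to PERT after Visit 13 (Protocol Table 3), so few 4.4 g/day events are likely to be open when a 6.7 g/day stage starts.

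Safety analysis is descriptive, so no test or sample size changes.

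**What to change.** Replace the fourth bullet of SAP 8.3 with: *A TEAE is attributed to the treatment being taken at onset, and to a later treatment only if it worsens in severity after that treatment starts.* Use the same rule for the SAE tables and for the 4.4 and 6.7 g/day extension stages. Flag in the AE listing every event ongoing at the switch. In the discontinuation tables, count an event under the treatment being taken when it led to discontinuation, so that such withdrawals are not lost.

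The cost is a short change to the SAP wording and one programming flag. The downside is that a few ongoing, non-worsening events leave the second treatment's column and are then visible only through the flag.

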### **5.6.2 MS1819/16/01 Phase 2a Study with MS1819**

An open-label, dose escalation Phase 2a study (MS1819/16/01) was conducted to investigate the safety of escalating doses of MS1819 in 11 patients with EPI caused by chronic pancreatitis or pancreatectomy.

The primary objective of this study was to investigate the safety of escalating doses of MS1819 (280 mg/day, 560 mg/day, 1120 mg/day, and 2240 mg/day). Each dose was given over a two-week period. A CFA was obtained at baseline after washout, and after each escalating dose period. Safety assessments included immunoallergic side effects, digestive symptoms, and clinical laboratory tests. The secondary objective of this study was to investigate the efficacy of MS1819 by assessment of CFA.

Eleven patients were enrolled into the study, and ten completed all doses. One patient withdrew during the 1120 mg/day dose level due to severe diarrhea. This was not assessed as related to study drug.

In the Intent-to-Treat population, mean CFA rose from a baseline of 46.1% to 62.4% at the highest dose ( $p = 0.001$ ). A number of symptoms improved comparing the highest dose to baseline, including stool consistency ( $p < 0.001$ ), number of bowel movements ( $p = 0.006$ ), steatorrhea ( $p = 0.008$ ), and abdominal pain ( $p = 0.148$ ). The treatment was well tolerated, with only two SAEs reported. Only one SAE was considered by the investigator to be possibly related to study drug, which was a patient with mild, transient elevations of liver enzymes. The elevations were between 2 and 3 X upper limit of normal (ULN), and lasted for about two weeks, a period of time that the patient was no longer receiving study drug. The patient had no symptoms of liver disease.

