TEAEs will be summarized for all subjects in the safety population. TEAEs will be summarized by treatment group for each dose in the crossover phase and for each dose in the extension phase. The total number of TEAEs occurring will be shown. The number and percentage of subjects experiencing any TEAE will also be provided. In addition, summary tables will reflect a count and percentage of subjects experiencing at least 1 TEAE in each system organ class and preferred term. All percentages will use the number of subjects in the safety population as the denominator. Therefore, if a subject has more than 1 AE within a system organ class, the subject will be counted only once in that system organ class. If a subject has more than 1 AE that codes to the same preferred term, the subject will be counted only once for that preferred term. Tabular summaries will be sorted by descending frequency by system organ class and by preferred term in the MS1819 treatment group.

Treatment-emergent AEs will be presented by treatment group and overall for the crossover phase and overall for the extension phase with percentages that use the number of subjects in the safety population as the denominator.

Treatment-emergent AEs will also be summarized by maximum relationship to study drug and maximum severity. Relationship to each study treatment (MS1819 and prestudy PERT [crossover phase only]) will be scored as Related or Unrelated. Severity will be rated as Mild, Moderate, or Severe. All percentages will use the number of safety subjects as the denominator. Summary tables will reflect a count and percentage of subjects experiencing at least 1 TEAE in each system organ class, preferred term and grouping, relationship, or severity. If a subject experiences more than 1 AE within a system organ class or preferred term, that subject will be counted only once for that event under the maximum severity or most related category for the study drug. Similarly, in the event that relationship or severity data are missing, the study analysis will follow the assumption of maximum relationship or severity in the summary tables. These summaries will be presented by treatment group and overall in the crossover phase and overall in the extension phase with percentages that use the number of subjects in the safety population as the denominator. The tabular summaries will be sorted by descending frequency by system organ class and by preferred term in the MS1819 treatment group.

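### SAP 8.3 assigns adverse events by the period in which they start, with no post-dose window and no washout, so delayed events of either treatment land under the other treatment or in follow-up with no named column.

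*SAP*

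**What the plan says.** Safety versus PERT is a primary objective (Protocol 6.1, SAP 2.1.1). SAP 8.1 has safety "summarized by actual treatment (MS1819 regardless of period vs. PERT regardless of period) allowing direct intrasubject comparison of the tolerability of MS1819 vs. PERT".

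The assignment rules are in SAP 8.3:

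- **Treatment-emergent events.** Events that occur or worsen "on or after date of first dose of study treatment in crossover phase period 1 will be considered to be TEAEs". No end date is set.
- **Period 2.** Events "after the end date of crossover period 1 study treatment and on or before the date of end of crossover period 2 study treatment" belong to period 2.
- **Follow-up.** Events after a subject's "last crossover study period will be classified as follow-up adverse events". For a subject who never starts period 2, this means everything after the end of period 1.
- **Changeover and overlap.** Untimed events on the crossover date go to period 1. Events occurring in both periods count in both.
- **Relatedness.** "Relationship to each study treatment (MS1819 and prestudy PERT [crossover phase only]) will be scored as Related or Unrelated".

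Tables are shown by treatment group and overall. The SAP text describes no follow-up column.

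Protocol 7.1 states that there is no washout. At the end of Visit 9 all patients resume or continue their prestudy PERT. Visit 10, about two weeks after the last dose, records adverse events and draws anti-LIP2 antibodies (Protocol 8.3.3).

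**The concern.** The columns of the adverse-event tables will be read as what happened on each treatment. With no interval between treatments and no post-dose window, an event that MS1819 causes with a short delay is not counted under MS1819. An event starting the day after the switch, and scored by the investigator as related to MS1819, is tabulated under PERT. In the other sequence, the same event leaves the two-column comparison. The mirror image holds for PERT in the patients who take it first.

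At stake is the within-patient tolerability comparison on which SAP 8.1 relies, in arms of about 15 patients. The trial also collects safety data at Visit 10 without the SAP text saying how those events enter that comparison.

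**Working it through.** **Step 1: trace the rules.** For a new event with a complete date, starting after the day of the last dose:

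| Situation | Where SAP 8.3 puts it |
|---|---|
| After MS1819 in period 1, then PERT | PERT column |
| After MS1819 in period 2 | Follow-up, no treatment column named |
| After MS1819 stopped in period 1, no period 2 | Follow-up, no treatment column named |
| After PERT in period 1, then MS1819 | MS1819 column |
| After PERT in period 2 | Follow-up, although the patient stays on PERT |

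The early-stopping path is realistic. In the OPTION trial, five patients discontinued during MS1819 and three during PERT (Protocol 5.6.3).

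**Step 2: size.** The plan states no figure to reproduce and gives no adverse-event rates, so the rates below are assumptions. Inputs from the documents are 15 patients per dose (SAP 2.6) and 1:1:1:1 allocation (SAP 2.4), giving 15/2 = 7.5 per sequence. Let aM and aP be mean on-treatment events per patient. Let dM and dP be mean delayed events per patient after the last dose of MS1819 or PERT.

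Case A: PERT does not stop after period 2, so it has a post-dose interval only in the PERT-MS1819 sequence.

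- SAP rule: MS1819 = 15aM + 7.5dP; PERT = 15aP + 7.5dM; follow-up = 7.5dM.
- By originating treatment: MS1819 = 15aM + 15dM; PERT = 15aP + 7.5dP.
- Distortion of MS1819 minus PERT = 7.5(dP - dM) - (15dM - 7.5dP) = 15dP - 22.5dM.

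Case B: delayed PERT events are also counted after a period 2 PERT course. The PERT total by origin becomes 15aP + 15dP, and the distortion is 7.5(dP - dM) - 15(dM - dP) = -22.5(dM - dP).

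The on-treatment rates cancel in both. A negative value favours MS1819. Events per 15 patients:

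| dM | dP | Case A | Case B |
|---|---|---|---|
| 0.2 | 0 | -4.5 | -4.5 |
| 0.2 | 0.1 | -3.0 | -2.25 |
| 0.2 | 0.2 | -1.5 | 0 |
| 0.1 | 0.2 | +0.75 | +2.25 |
| 0 | 0.2 | +3.0 | +4.5 |

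The sign changes at dP = 1.5dM in Case A and at dP = dM in Case B.

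**Step 3: weight of one patient.** 1/15 = 6.7 percentage points. With about 36 enrolled (Protocol 7.3.1), or 18 per dose, it is 1/18 = 5.6 points. This shows how sensitive a column is. It does not estimate bias.

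**The case against.** The strongest reply is that the rule is even-handed. Period 1 PERT events move into the MS1819 column just as period 1 MS1819 events move into the PERT column, and allocation is balanced. This largely stands: a reader who follows only the MS1819-PERT sequence might infer a one-sided bias toward MS1819, and the documents do not support that. What survives is an imbalance of opportunity. MS1819 is followed by a post-dose interval in both sequences and PERT in only one. On the other side, patients in follow-up are on PERT, so that class also keeps on-PERT events out of the PERT column.

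Two pieces of protocol background may also tempt a stronger reading. In the earlier chronic pancreatitis study, liver-enzyme elevations lasted about two weeks, "a period of time that the patient was no longer receiving study drug". No onset date is given, and SAP 8.3 assigns by onset or worsening, so this may not be an event the rule would move. Protocol 7.3.4 names immunoallergic reactions as a reason for removal but does not call them delayed.

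There is some mitigation. Relatedness is scored for each treatment, all adverse events are listed, and the DSMB Chairperson receives SAE reports in real time. Because treatment-emergent events have no end date, follow-up events may appear in the overall column. The Table Display Specifications are an attachment not available here, so a follow-up column in them cannot be excluded. None of this moves an event out of the wrong treatment column, and SAP 10.1 has the DSMB's planned end-of-study review use a subset of the same analyses.

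**Conclusion.** The mechanism is confirmed from the text. New events after the day of the last MS1819 dose go to PERT or to follow-up with no named column, whatever the relatedness score, and post-PERT events in period 2 go to MS1819.

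It would be too strong to say that the MS1819 column can never hold a post-dose event. Untimed events on the crossover date go to period 1, the end of period 2 is also judged by date, events in both periods count in both, and partial start dates can be imputed into both periods (SAP 8.1).

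The direction is open. Over the assumed rates the distortion runs from -4.5 to +4.5 events per 15 patients. With equal rates of 0.2 it is -1.5 if PERT is treated as continuing after period 2, and zero if it is not. A lean toward MS1819 is therefore plausible but not shown.

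This does not undermine a descriptive phase 2 safety analysis. It does concern a stated rule that can misplace events in a primary safety comparison and that is cheap to supplement.

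**What to change.** Keep the on-treatment table as planned and add to SAP 8.3:

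1. Follow-up treatment-emergent events tabulated by the treatment last taken, including patients who stop in period 1.
2. In the relatedness tables, an event scored Related to a treatment counted under that treatment, whatever period it started in.
3. One supportive table with the same short, pre-specified post-dose window for both treatments. An event inside the window after a switch is counted under both.

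The window should not apply to MS1819 alone. Fourteen days for MS1819 only would give it 21 + 14 = 35 days at risk against 21 for PERT, and would cover 14/21, or two-thirds, of the PERT period in the MS1819-PERT sequence. Its length should also fit the observation time. If Visit 9 starts on Day 43 and lasts 7 days it ends on Day 49, and Visit 10 at its earliest (Day 54) is then 54 - 49 = 5 days later.

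The cost is SAP wording and one or two extra tables from data already collected. The supportive table will contain some double-counted events and some due to background disease, and should be labelled accordingly.
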